10.3.4 Deviation(s) from the original statistical plan

Deviations of the original statistical plan will be reported according to chapter 2.10.

10.4 Handling of missing data and drop-outs

Intention to treat analysis is planned to account for missing data.

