5. STUDY DESIGN

5.1 General study design and justification of design

This study is designed as a prospective randomized controlled clinical trial. 50 persons over 18 and below 75 years of age with low back pain of more than 4 weeks without any “red flags” (i.e., infection, trauma, fractures, inflammatory spondylarthropathies) as well as 20 asymptomatic controls meeting the inclusion criteria are included. Study visits will take place in the morning at the same time.

Patients and controls report baseline information and receive a standardized baseline examination. Patients’ skin above the interspinous ligament causing the most pain upon palpation by the examiner is marked with a pen. The examiner is blinded to the intervention that follows.

Patients and controls are evaluated in the MRI-Scanner lying supine prior to intervention. The radiologist will perform a preliminary viewing of the MRI sequence to screen for contraindications to SMT (e.g. tumors, infection, fractures, severe nerve compression). Patients with contraindications for SMT will be excluded from the study.

Patients will be randomized using stratified randomization to receive either an SMT intervention in right and left side-lying position at the segment of the marked interspinous ligament, or receive a control intervention in right and left side-lying position. The chiropractor administering the intervention is blinded to clinical and radiological information. After this, patients undergo 3 sequential MR-imaging rounds. Once imaging is complete, the subjects exit the scan room and provide information on post-intervention pain-intensity.

MRI-quantified changes in diffusion and perfusion of intervertebral discs with and without degenerative changes and of adjacent spinal muscle tissue after SMT intervention are assessed and compared between patients and controls.

In order to assess the repeatability of IVIM imaging in quantifying perfusion in musculoskeletal tissues, 20 controls will undergo a separate procedure consisting of a baseline diffusion- and perfusion-weighted MRI, which is repeated after 20 minutes of lying in a supine position. In order to assess diurnal changes in perfusion and diffusion parameters in musculoskeletal tissue, controls will present for a third MRI approximately 10 hours later, after partaking in activities of daily life as normal, but excluding strenuous physical activity.

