7.5 Data Collection and Follow-up for withdrawn participants

The data of withdrawn participants is going to be excluded from the final analysis.

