10.3 Planned Analyses

Distributions of the ADC and perfusion coefficient obtained at the two time points (before and after intervention) will be tested for the assumptions of normality using the Shapiro-Wilk test. In case of non-normality, data transformation will be used to normalize data. Should this not be possible, non-parametric tests will be used. Two separate repeated measures analysis of variance (ANOVA) will be used to test for effects of time (pre- vs. post-intervention) on ADC and perfusion coefficients with intervention (experimental vs. control intervention) and group (degenerated vs. non-degenerated painful segments) as between-subject variables.

We will estimate the repeatability of IVIM-MRI in measuring perfusion in musculoskeletal tissue using paired t-tests and the intraclass correlation coefficient ICC⁴⁹.

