10.3.1 Dataset to be Analysed, analysis populations

The statistician will supervise the analysis as described in 11.4.

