10.3.2 Primary Analysis

Our hypothesis is that a spinal segment receiving an SMT-intervention will show a change in the diffusion and pseudodiffusion coefficient that is significantly higher than a spinal segment receiving a control intervention. Distributions of the ADC and perfusion coefficient obtained before and after intervention will be tested for the assumptions of normality using the Shapiro-Wilk test. In case of non-normality, data transformation will be used to normalize data. Should this not be possible, non-parametric tests will be used. Two separate repeated measures analysis of variance (ANOVA) will be used to test for effects of time (pre- vs. post-intervention) on ADC and perfusion coefficient with intervention (experimental vs. control intervention) and group (degenerated vs. non-degenerated painful segments) as the between-subject variables.

The PI will supervise the primary analysis as described above. It will be analyzed using SPSS (version 23) at the end of the recruitment period and after obtaining all necessary data.

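### Section 10.4 relies on intention to treat to handle missing data, but the planned pre/post ANOVA and the exclusion of withdrawn participants make the primary analysis complete-case

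*Combined protocol and SAP*

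**What the plan says.** All references are to the combined protocol and SAP.

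- **Missing data.** The whole of section 10.4 is: "Intention to treat analysis is planned to account for missing data". No imputation, likelihood-based model, sensitivity analysis or rule for unusable images appears there or elsewhere.
- **Primary model.** Section 10.3.2 states: "Two separate repeated measures analysis of variance (ANOVA) will be used". Time is pre against post, and intervention and degeneration are between-subject factors. Section 10.3 describes the values as "obtained at the two time points (before and after intervention". If normality fails and transformation does not help, non-parametric tests are used, also without a missing-data rule.
- **Software.** Section 10.3.2: "It will be analyzed using SPSS (version 23) at the end of the recruitment period". No procedure or missing-value option is named.
- **Analysis population.** Section 10.3.1 carries that heading but says only: "The statistician will supervise the analysis as described in 11.4". Section 11.4 concerns audits. If the reference is one chapter out, as those in 7.2.1 and 11.5 are, it leads back to the sentence in 10.4.
- **Withdrawals.** Section 7.5: "The data of withdrawn participants is going to be excluded from the final analysis". Section 8.2.5 repeats this.
- **Scans.** Section 5.1, after the intervention: "After this, patients undergo 3 sequential MR-imaging rounds". The visit procedures in 8.3.2 mention only a second round. No section says which scan, or what summary, is the post value.

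**The concern.** The plan names a principle where a method is needed. A patient can be randomised, treated and never withdrawn, yet have no usable post-intervention value because of motion, a failed parameter fit or a session cut short. Nothing in the plan keeps that patient in the comparison. For patients who do withdraw, 7.5 and 8.2.5 require the opposite of intention to treat.

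The balance created by randomisation is at stake. Section 8.3.2 places randomisation after the first MRI, so loss after randomisation falls mainly on post-intervention scans, where the allocated intervention could influence it. Section 5.2.2 says patients cannot be blinded, and section 3.7 says SMT is commonly followed by soreness and local discomfort. If loss is related to both arm and outcome, the patients who remain are no longer a randomised comparison, while the plan describes the analysis as intention to treat.

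**Working it through.** **Step 1. What the planned model needs from each patient.** With two time points and two arms, the time-by-intervention F statistic equals the square of the two-sample t statistic on change (post minus pre). On simulated data with 25 per arm, both came to 0.0135. A patient without a pre or a post value has no change score and contributes nothing to this test. With no imputation planned, the analysis is complete-case. The plan does not use that term; it follows from the named model and the absence of any alternative.

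**Step 2. The sections side by side.**

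| Section | Effect on who is analysed |
|---|---|
| 10.4 | Claims intention to treat |
| 10.3, 10.3.2 | Only patients with both a pre and a post value |
| 7.5, 8.2.5 | Withdrawn participants left out |
| 10.3.1 | No population defined |

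Some reasons for withdrawal in 6.4 arise before randomisation, such as a contraindication seen on the first MRI, and leaving those patients out does not breach intention to treat. Others, such as withdrawal of consent or non-compliance, can arise afterwards. Sections 7.5 and 8.2.5 make no distinction.

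**Step 3. The plan's own power figure.** Section 10.2 gives 25 per group, effect 0.9, alpha 0.05 and power 0.8. Reading 0.9 as a standardised difference, a two-sided t-test with 25 per arm has power 0.877, and 21 per arm would be enough for 0.8. The stated figure is not reproduced: 25 is more than these inputs require. That is a separate matter and does not affect this point.

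**Step 4. Power under loss.** The documents give no loss rate. Assume a probability p that a scan is missing or unusable, independent between scans, with two scans needed:

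proportion lost = 1 − (1 − p)²

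| p (assumed) | Lost | Left of 50 | Arms | Power at 0.9 |
|---|---|---|---|---|
| 0% | 0% | 50 | 25/25 | 0.877 |
| 3% | 1 − 0.97² = 5.9% | about 47 | 24/23 | 0.855 |
| 5% | 1 − 0.95² = 9.8% | about 45 | 23/22 | 0.839 |

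These losses are on the high side, because they count the baseline scan, which is taken and previewed before randomisation.

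**Step 5. Bias, for illustration only.** If a fraction m of the SMT arm is lost, and the change in those patients is k SD lower than in those observed, the observed SMT mean is too high by m × k.

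- m = 10%, k = 0.5: 0.05 SD, and 0.05/0.9 = 6% of the planned effect.
- m = 3/25 = 12%, k = 1: 0.12 SD, or 13%.
- m = 20%, k = 1: 0.20 SD, or 22%.

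Both m and k are assumptions; the documents give neither.

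**The case against.** The strongest reply is that the plan is brief rather than wrong: it names SPSS but no procedure or deletion rule, so complete-case analysis is an inference. That is true of the wording, but the inference is short. A pre/post ANOVA with no rule for missing values can use only patients who have both values, and 7.5 and 8.2.5 state an exclusion outright.

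Three stronger readings are tempting, and the documents do not support them.

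- **That every patient with any missing scan is dropped.** Requiring all four scans gives 1 − 0.97⁴ = 11% and 1 − 0.95⁴ = 19% lost. But 10.3 and 10.3.2 describe two time points, and nothing says how three post-intervention rounds become one value. A patient missing one round might still be analysed.
- **That the trial falls below its stated power of 0.8.** Even the four-scan model at 5% leaves about 41 of 50 patients, and 21/20 gives 0.802. A value of 0.79 needs exactly 20 per arm.
- **That arm-related loss is to be expected.** Section 6.1 excludes people who cannot tolerate SMT or lie on their side without pain, and the patients' pre and post scans fall within one visit. Such loss is possible, but its size and direction are unknown.

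It is also fair to say that no model recovers much from a patient with only a baseline scan.

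**Conclusion.** The point holds. Intention to treat, as used in 10.4, does not account for missing data. The ANOVA in 10.3.2 together with the exclusions in 7.5 and 8.2.5 produces a complete-case primary analysis that contradicts it. This is more than a missing detail, because following the plan literally yields a result that does not match its description.

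The main consequence is possible bias from loss after randomisation, which cannot be sized from the documents. With 25 per arm, a few selective losses could move the estimate by around a tenth of the planned effect, but that is an illustration and not a forecast. Power is a minor matter: about 0.86 to 0.84 at an assumed 3% to 5% independent loss per scan, with 0.9 read as a standardised difference and a two-sided t-test on change. The plan should be corrected before allocation is unblinded, since a missing-data rule chosen afterwards would carry little weight.

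**What to change.** 1. Replace the sentence in 10.4 and define the population in 10.3.1: all randomised patients, analysed in the arm to which they were allocated.
2. Amend 7.5 and 8.2.5 in the same edit so that data collected before withdrawal are kept where consent allows. Changing 10.4 alone would leave those sections forbidding it. Section 6.4 already provides for anonymising data after evaluation when consent is revoked, so the three sections should be reconciled.
3. Replace each ANOVA with a linear mixed model (SPSS MIXED) on the baseline scan and all usable post-intervention scans. Set the baseline mean equal across arms, which is justified because the baseline scan precedes randomisation, and keep the planned degeneration factor.
4. Name one primary post-intervention contrast, for example the between-arm difference in the mean of the three post scans. A patient missing one post scan then stays in the comparison; a patient with only a baseline scan adds little to it.
5. Add one sensitivity analysis that shifts the missing SMT-arm values in the unfavourable direction over a range stated in advance, for example 0 to 1 SD of change.
6. Report unusable and missing scans by arm, with reasons.

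The cost is revised wording and slightly more programming, with no new data or software. The downside is that the mixed model assumes data are missing at random; item 5 shows how far the result depends on that.

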11. QUALITY ASSURANCE AND CONTROL

11.1 Data handling and record keeping / archiving

Data is exclusively stored using the secured REDCap® electronic data capture tool⁵⁰. When the study is terminated, data will be stored in the same system. Data can only be accessed by defined persons that have contributed to the project. Radiological data will be stored in the institution's PACS system according to the institutional standard at the University Hospital Balgrist.

All study data are encrypted in an automatically secured online processing system (REDCap® electronic data capture system). The principal investigator is responsible for data collection. She keeps the screening log, which guarantees the confidentiality of data by the use of participant ID numbers. The participant ID numbers are automatically assigned in consecutive ascending form by the REDCap® system. For the purpose of fulfilling their task, the principal investigator grants the necessary access authorization in the form of user log-in and password to the study staff (see Staff List). Thus, the data cannot be altered in any way by unauthorized persons. In the REDCap® system, all relevant processing operations are documented in a user-specific manner in order to ensure traceability. This is done by means of registration software, which records who has edited which data at which time. REDCap® has a database server, which is located in highly modern, secure server rooms in Rümlang and Altstetten. The RED-Cap® database is secured daily by backup. All transaction logs between two consecutive backups are kept for one week. All study programs in REDCap® are kept for an unlimited time, but at least for 10 years. Data collected in the course of this study are available for inspection or inspection by monitors, independent EC and competent authorities.

11.1.1 Case Report Forms

An electronic Case Report Form (eCRF) will be generated for every participant and all data relevant to the study is going to be recorded by authorised persons (identifiable). The REDCap® electronic data capture tool is hosted by the University Hospital Balgrist. All persons (participants, patients, excluded patients) will be documented in a screening log. Participating participants/patients will be registered in an enrolment log (patient identification key). The investigator is responsible for correct and complete data input into the study-specific database. Corrections can only be made by authorised persons and have to be justified. Older versions are not overwritten and stay accessible. All data and corrections are logged with date, time and person.

11.1.2 Specification of source documents

All data appearing in the eCRF can be found in the patient's medical record via the proprietary hospital information system. Source data only found in the CRF has to be clearly defined and labelled.

11.1.3 Record keeping / archiving

All study data is going to be archived for a minimum of 10 years (Art.45 KlinV) after study termination or premature termination of the clinical trial. Data is stored using the proprietary hospital information system and REDCap® electronic data capture tool hosted at the University Hospital Balgrist⁵⁰.

11.2 Data management

11.2.1 Data Management System

Study data is going to be recorded and managed using REDCap® electronic data capture tools hosted at University Hospital Balgrist⁵⁰.

11.2.2 Data security, access and back-up

Only authorized medical personnel are granted access to study data. Records are going to be hosted using REDCap® electronic data capture tools at the University Hospital Balgrist⁵⁰.

11.2.3 Analysis and archiving

Details of data management procedures can be found at⁵⁰.

11.3 Monitoring

11.3.1 Outline of the monitoring strategy

One monitoring visit at the investigator's site prior to the start, one visit within one year after inclusion of the first participant and approximately once visit per annum during the course of the study will be organised by the Sponsor. Furthermore, there will be a monitoring visit at the study end. During the monitoring, all documents including source data/documents will be accessible for the monitor and all questions will be answered.

Study period	Time	Monitoring
Before study start	Dec 2018	Information about study conduct concerning data sampling and safety reporting. Monitor controls if 
 • Documents are approved by KEK • Documents are at site • Investigators are familiar with study protocol and safety reporting • Investigators know their duties and responsibilities
After inclusion of first patient	Within 1 year	All subjects: SDV for existence and informed consent First trial participant and at least 10% of trial participants recruited at the time of the visit, as far as available: eligibility, primary endpoint, SAEs
Further visits	1 per annum	All subjects: SDV for existence and informed consent At least 10% of trial participants recruited at the time of the visit, as far as available: eligibility, primary endpoint, SAEs, additional protocol-specific safety parameters.
Study end	Dec 2020	Close out visit to control for completeness of source data

11.4 Audits and Inspections

Direct access to source documents will be permitted for purposes of audits and inspections for eligible authorities (swissmedic, independent ethics committees). Auditors/Inspectors are going to be granted full access to medical records, documents as well as signed consent forms via the implemented "audit trail" of the RED-Cap® electronic data capture tool or the proprietary hospital information system⁵⁰.

11.5 Confidentiality, Data Protection

Direct access to source documents will be permitted for purposes of monitoring (12.3), audits and inspections (12.4). Only authorised medical personnel are going to have access to protocol, dataset and statistical code during and after the study.

11.6 Storage of biological material and related health data

Health data will be stored as described in chapters 12.2 and 12.2.

Whole blood is withdrawn from fasting patients using serum collection tubes. Blood samples are allowed to clot at room temperature for 30-60 min and then centrifuged at 2500 x g for 10 min at 4°C. The resulting serum supernatant is stored in aliquots first at -20°C and transferred within 2-20 hours to -80°C. All samples will be stored in the *Swiss Center for Musculoskeletal Biobanking (SCMB), Balgrist Campus AG*, and analysed together at the end of the recruitment period. Serum samples are taken for the assessment of selected inflammatory molecules. Serum concentrations of 8 biomarkers will be measured using electrochemiluminescent based multi-array immunoassays from MesoScale Discovery (MSD, Rockville, MD, USA) following the protocol of the manufacturer. Remaining serum will be encoded and stored for a minimum of 10

years at -80° (general consent).

12. PUBLICATION AND DISSEMINATION POLICY

The results of this trial are going to be published in a peer reviewed medical journal.

13. FUNDING AND SUPPORT

13.1 Funding

A part of the cost for the experimental intervention (MRI) is defrayed by a financial grant of CHF 15'000 provided by the Zürcher Verein Pro Chiropraktik. The study intervention will be free of charge for the study participants and their health insurances. The majority of costs (staff and standard equipment) will be covered by the participating institution (Balgrist).

14. INSURANCE

The standard Balgrist research insurance (as already presented to the KEK) is applicable.

